PET	Positron emission tomography
MRI	Magnetic resonance imaging
AD	Alzheimer's disease
MCI	Mild cognitive impairment
AD	Alzheimer's disease
SUVR	Standardized uptake value ratio
¹⁸ F-THK-5351	((S)-1-(fluoro- ¹⁸ F)-3-((2-(6-(methylamino)pyridin-3-yl)quinolin-6-yl)oxy)propan-2-ol).
mCi	millicurie
MBq	Megabecquerel
μSv	microSievert
μGy	microGray

Study Summary

Title	Imaging tau in Alzheimer's disease and normal aging
Short Title	Imaging tau in Alzheimer's disease and normal aging
Protocol Number	AAAQ7868
Phase	II
Methodology	
This is a single center PET study.
 
Screening will include history and physical examination, brain MRI, and neuropsychological examination. Subjects who meet criteria for Alzheimer's disease (AD) or mild cognitive impairment (MCI), or who are cognitively normal will then have one brain PET scan with ¹⁸F-THK-5351. Vital signs will be checked prior to injection of ¹⁸F-THK-5351, then at the completion of the PET scan.
 
Subjects will have the option of having a lumbar puncture to measure CSF concentrations of markers of inflammation and neurodegeneration.

Study Duration	5 years
Study Center(s)	Taub Institute, CUMC
Objectives	The primary objective is to determine the relationship between tau, normal aging, and Alzheimer's disease.
Number of Subjects	Up to 60 of these subjects will have ¹⁸ F-THK-5351. PET. Subjects will be 50 years and older. Thirty subjects will have normal cognition and the other thirty will have cognitive impairment.

Diagnosis and Main Inclusion Criteria	
Inclusion criteria:
 
 1. Age 50 and older 2. Meet criteria for either a) amnestic mild cognitive impairment (single or mixed domain) or mild Alzheimer's disease, or b) have no cognitive impairment, based on history, exam, neuropsychological testing, and consensus diagnosis. MCI and mild AD patients must have Clinical Dementia Rating scale score of 0.5 or 1. Unimpaired subjects must have Clinical Dementia Rating scale score of 0. 3. Subjects unable to provide informed consent must have a surrogate decision maker 4. Written and oral fluency in English or Spanish 5. Able to participate in all scheduled evaluations and to complete all required tests and procedures. 6. In the opinion of the investigator, the subject must be considered likely to comply with the study protocol and to have a high probability of completing the study. 
Exclusion criteria:
 
 1. Past or present history of certain brain disorders other than MCI or AD. 2. Certain significant medical conditions, which make study procedures of the current study unsafe. Such serious medical conditions include uncontrolled epilepsy and multiple serious injuries. 3. Contraindication to MRI scanning 4. Conditions precluding entry into the scanners (e.g. morbid obesity, claustrophobia, etc.). 5. History of kidney disease or presence of impaired kidney function based on laboratory tests at screening visit. Benign or resolved kidney conditions such as uncomplicated kidney stones or treated infection would be allowed if kidney function is normal at screening visit. 6. History of liver disease or presence of impaired liver function based on laboratory tests at screening visit. Benign or resolved liver conditions such as uncomplicated cysts or resolved viral infections would be allowed if liver function is normal at screening visit. 7. Participation in the last year in a clinical trial for a disease modifying drug for AD. 8. Inability to have a catheter in subject's vein for the injection of radioligand. 9. Inability to have blood drawn from subject's veins.
Study Product, Dose, Route, Regimen	¹⁸ F-THK-5351, up to 5 mCi (185 MBq), IV, total of one injection.

Duration of administration	A single dose of radioligand will be injected over 1 minute for each PET scan.
Reference therapy	N/A
Statistical Methodology	
Comparing PET imaging among groups The primary outcome measure will be regional standardized uptake value ratio (SUVR) values for ¹⁸F-THK-5351 using cerebellum as reference region. Multiple brain regions will be measured, with particular attention to medial temporal cortex structures such as hippocampus and entorhinal cortex. Analysis will be performed using a one-way ANOVA with cognitive status (AD vs. MCI vs. normal) as independent variable. Effect of age and education on ¹⁸F-THK-5351 will be determined in post-hoc analysis.
 
Sample size determination Results from a small published study showed greater ¹⁸F-THK-5351 binding in hippocampus in AD patients (n = 3) than controls (n = 3), with effect size of 1.95. This would allow us to detect differences in ¹⁸F-THK-5351 between AD patients and controls in hippocampus with n = 10 subjects per group. However, we don't know the effect size when MCI patients are compared to AD patients and when MCI patients are compared to controls. We wish to scan up to 60 subjects total (30 impaired and 30 unimpaired) to ensure power to see effect on ¹⁸F-THK-5351 binding between groups.
 
We will also perform linear regression to look for correlations between change in ¹⁸F-THK-5351 binding and cognitive scores, CSF concentration of biomarkers of inflammation and neurodegeneration, and atrophy measured with MRI.

1 Introduction

This document is a protocol for a human research study. This study is to be conducted according to US and international standards of Good Clinical Practice (FDA Title 21 part 312 and International Conference on Harmonization guidelines), applicable government regulations and Institutional research policies and procedures.

1.1 Background

1.1.1. Background on Alzheimer's disease

While amyloid plaques are a pathological hallmark of Alzheimer's disease (AD), whether β -amyloid is the causal agent of neurodegeneration in AD remains unclear. Evidence supporting the hypothesis that amyloid is a primary contributor to AD pathogenesis (the amyloid-first hypothesis) include the finding that genetic mutations responsible for inherited forms of AD cause increased amyloid production. Studies using positron emission tomography (PET) to measure amyloid plaque burden in vivo have demonstrated amyloid positivity before obvious atrophy or cognitive decline in healthy older controls. While tau positive neurofibrillary tangles represent the second hallmark of AD, tau mutations are seen in patients with variants of frontotemporal dementia, not AD. The propagation of tau pathology is thought to follow amyloidosis, suggesting amyloid in some way induces tau mediated degeneration. However, the link between amyloid and tau not clear as there are spatial and temporal distinctions. For example, bulk of amyloid burden in medial parietal cortex and frontal cortex early on, while tau burden begins in medial temporal cortex.

While β -amyloid has been shown to have direct neurotoxic effects in vitro, these effects are seen at concentrations of β -amyloid much higher than found in human brain[1]. Therefore, amyloid may not confer significant direct toxicity. In addition, autopsy findings of pre-tangle pathology occurring in midlife prior to amyloidosis[2] suggest that tauopathy may begin prior and independent to significant amyloid plaque deposition. Since amyloid burden correlates poorly with cognition[3], tau may be a more important mediator of neurodegeneration in AD.

4.1.1. Background on tau pathology in neurodegenerative diseases.

Deposition of hyperphosphorylated tau protein is observed in several neurodegenerative diseases including Alzheimer's disease, progressive supranuclear palsy, corticobasal degeneration, chronic traumatic encephalopathy, and frontotemporal lobar degeneration [4]. Tau is a microtubular protein and its native function is to provide structural support to neurons. Paired helical filaments composed of dysfunctional tau protein are found in several neurodegenerative diseases. In Alzheimer's disease, the clinical progression of dementia has been shown to correlate with the amount and topographical spread of tau throughout the brain. Therefore, detecting and quantifying tau aggregate load in brain would have diagnostic and prognostic potential in clinical management of several neurological diseases. As disease modifying drugs that target tau are being developed, there is a critical need for a reliable method of detecting tau aggregates to confirm pathology in patients entering clinical trials.

4.1.2. Background on PET imaging of tau

Positron emission tomography (PET) imaging allows in vivo measurement of protein density after administration of radiolabeled ligands that bind to the target protein. ^{18}F -FDDNP has demonstrated increased binding in patients with tauopathies such as Alzheimer's disease [5-6].

8] and progressive supranuclear palsy [9]. Reports using this radioligand found increased binding in former NFL players in medial temporal and brainstem structures known to be affected in chronic traumatic encephalopathy [10, 11]. However, FDDNP binds to both fibrillar amyloid and tau, so the PET signal is nonselective and the greater density of amyloid plaque than tau-positive tangles is expected to confound measurement of tau in patients with co-pathology. The more recently developed radioligand ¹⁸F-T807 (now ¹⁸F-AV-1451) has been shown to have greater affinity for tau aggregates than amyloid plaques. While only a small number of studies using ¹⁸F-AV-1451 have been published to date [12, 13], several clinical trials are currently employing this radioligand.

¹¹C-PBB3 has high affinity and high selectivity for tau [14]. Human studies to date have included healthy controls, patients with Alzheimer's disease, and one patient with corticobasal syndrome. However, ¹¹C-PBB3 has limitations in that radiometabolites enter the brain [15] and the radioligand undergoes photo-isomerization in fluorescent light [16].

Other alternative tau radioligands include ¹⁸F-THK-5117, which has greater binding in AD patients than controls in expected distribution of tangle pathology [17]. However, this compound has a relatively high amount of white matter binding that could confound accurate quantification of tau aggregation in vivo. Nevertheless, ¹⁸F-THK-5117 binding increases in patients with AD, but not healthy controls over time, and this increase correlates with worsening of clinical symptoms[18].

¹⁸F-THK-5351 is a recently developed radioligand with lower nonspecific binding than ¹⁸F-THK-5117. Ex vivo studies show that binding of ³H-THK-5351 colocalizes to tau immunostaining in AD brain tissue, with lower white matter binding than seen with the earlier tau radioligand THK-5117[19]. Therefore, this recently developed radioligand has promise for reliable quantification of tau pathology in Alzheimer's disease and other tauopathies.

1.2 *Investigational Agent*

¹⁸F-THK-5351 is a PET radioligand that binds to paired helical filament tau aggregates. This radioligand has only been used for research purposes. ¹⁸F-THK-5351 will be administered in tracer doses ($\leq 10 \mu\text{g}$) at activity of up to 5 mCi (185 MBq) per injection.

2 Study Objectives

- 2.1. The primary objective is to determine the extent and spatial distribution of tau at different stages along the cognitive spectrum of aging (cognitively normal older adults, adults with mild cognitive impairment, and adults with Alzheimer's disease dementia).
- 2.2. Secondary objectives are to determine how ¹⁸F-THK-5351 binding in brain relates to cognitive performance, amyloid binding, atrophy on MRI, and CSF concentrations of markers of inflammation and neurodegeneration.

3 Study Design

3.1 General Design

3.1.1. Subject recruitment and screening procedures

Men and women age 50 and older will be recruited from the CUMC Washington Heights-Inwood Community Aging Project (known locally as WHICAP, R01 AG037212, PI [name]), the CUMC Alzheimer's Disease Research Center (ADRC), and [name] Questionable Dementia 2 (QD2) cohort, and CUMC clinics. Subjects may also be co-enrolled in Columbia University Medical Center protocols AAAO1151 (PI [name]), AAAO9758 (PI [name]), AAAI2752 (PI [name]), AAAQ8249 (PI [name]), and AAAQ8096 (PI [name]). Recruitment may come from additional research cohorts, as this protocol will encourage data sharing to reduce the total number of subjects that require ¹⁸F-THK-5351 imaging for project completion. Only subjects from established research cohorts that previously consented to be contacted about future research studies will be approached about this study. Informed consent will be obtained prior to study enrollment.

For subjects with cognitive impairment, prior to obtaining informed consent, a licensed physician who is not listed as personnel on this protocol will determine whether the subjects has capacity to provide their own consent. If the subject lacks consent, a legally authorized representative will be required to provide consent for the subject.

Up to 60 subjects will undergo screening including history, physical examination, routine laboratory studies, neuropsychological testing, and brain MRI. Subjects will be identified as either cognitively normal or cognitively impaired in consensus conference. Subjects must have Clinical Dementia Rating scale score of 0.5 or 1 and meet clinical criteria for either amnestic MCI (single or multiple-domain)[20] or Alzheimer's disease[21] to be included in the cognitively impaired category.

Target sample size is 30 elders with impairment and 30 elders without impairment (60 subjects total).

3.1.2 Neuropsychological data analysis

Selected neuropsychological tests scores will be combined into four composite scores (memory, language, executive/speed, and visuospatial). Memory testing will include Selective Reminding Test and Benton Visual Retention Test (BVRT), Recognition Memory Multiple Choice version. Z-scores for each cognitive measure will be calculated and averaged to create a composite z-score for each domain. These factor domain scores will be subsequently averaged to produce a composite cognitive z-score to indicate mean cognition. Higher z-score indicates better cognitive performance.

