4.1 Inclusion Criteria

1. Age 50 and older
2. Meet criteria for either a) amnestic mild cognitive impairment (single or mixed domain) or mild Alzheimer's disease, or b) have no cognitive impairment based on history, exam, neuropsychological testing, and consensus diagnosis. MCI and mild AD patients must have Clinical Dementia Rating scale score of 0.5 or 1. Unimpaired subjects must have Clinical Dementia Rating scale score of 0.
3. Subjects unable to provide informed consent must have a surrogate decision maker
4. Written and oral fluency in English or Spanish
5. Able to participate in all scheduled evaluations and to complete all required tests and procedures.
6. In the opinion of the investigator, the subject must be considered likely to comply with the study protocol and to have a high probability of completing the study.

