BVRT Matching, multiple-choice version, Boston Naming Test, 15 selected items, The Controlled Word Association Test and Category naming: Animals, Food and Clothing, Complex Ideational Material Subtest of the Boston Diagnostic Aphasia Evaluation (BDAE): first 6 items, The Color Trails Test part 1, WAIS-R Similarities, and Color Trails part 2. At minimum, subjects will receive testing in Selective Reminding Test, Trail Making Test, and Verbal Fluency (CFL, and Animals). Raw scores and demographically corrected T-scores (age, years of education, sex, and ethnicity) will be determined. Subjects will also undergo University of Pennsylvania Smell Identification Test (UPSIT), a non-invasive test that measures odor identification abilities.

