7.2 Statistical Methods

The primary outcome measure will be regional standardized uptake value ratio (SUVR) values for ¹⁸F-THK-5351 using cerebellum as reference region. Multiple brain regions will be measured, with particular attention to medial temporal cortex structures such as hippocampus and entorhinal cortex. Analysis will be performed using a one-way ANOVA with cognitive status (AD vs. MCI vs. normal) as independent variable. Effect of age and education will be determined in post-hoc analysis.

Regression models will be fit for ¹⁸F-THK-5351 binding as dependent variable and cognitive scores, voxel count on MRI, and CSF concentrations of markers of inflammation and neurodegeneration as independent variables.

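### The plan does not say whether the cognitive composites start from raw or demographically corrected scores, and the tau-cognition regression names no demographic or test-language term, so its slope is open to confounding by age.

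*Combined protocol and SAP*

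**What the plan says.** All references are to the combined protocol and SAP.

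- **Building the composites (3.1.2).** Four domain scores are formed: "Z-scores for each cognitive measure will be calculated and averaged to create a composite z-score for each domain". The global score follows: "These factor domain scores will be subsequently averaged to produce a composite cognitive z-score to indicate mean cognition". Neither sentence says whether the z-scores start from raw or corrected scores, or which population they are standardised to.
- **Scores available (4.3).** "Raw scores and demographically corrected T-scores (age, years of education, sex, and ethnicity) will be determined". No section assigns the T-scores to an analysis. Test language is not among the corrected factors.
- **Tau-cognition model (7.2).** "Regression models will be fit for ¹⁸F-THK-5351 binding as dependent variable and cognitive scores, voxel count on MRI, and CSF concentrations" of inflammation and neurodegeneration markers as independent variables. No demographic term, and no choice among the cognitive scores, is given.
- **Age and education (7.2).** "Effect of age and education will be determined in post-hoc analysis". This follows the group ANOVA. The Study Summary makes its object explicit: "Effect of age and education on ¹⁸F-THK-5351 will be determined in post-hoc analysis". It is not tied to the cognition regression.
- **Sample (3.1.1, 4.1).** Subjects are 50 or older with no upper age limit, 30 impaired and 30 unimpaired, and the language criterion is "Written and oral fluency in English or Spanish".
- **Status of the question (2.2).** How binding relates to cognitive performance is a secondary objective.

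**The concern.** Two analysts could follow this text and fit different models: composites from raw or from corrected scores, and a regression with or without demographic terms. That choice would remain open after the data are seen.

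It matters because the least adjusted reading, raw-based composites in the regression exactly as listed, does not isolate a tau-cognition relation. Age can plausibly raise binding and lower test scores. Left out of the model, it produces a negative slope even where tau and cognition are otherwise unrelated. Schooling or test language may move the scores without moving binding; that adds noise and weakens a true slope. At stake is the interpretation of the cognition part of a secondary objective, in a study whose stated aim sets normal aging beside Alzheimer's disease.

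**Working it through.** **The plan's own figure.** None exists for this analysis. The only sample-size figure (7.1: 10 per group at effect size 1.95) concerns hippocampal binding in AD against controls and does not bear on this point.

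**Inputs.** From the documents: n = 60 (the planned maximum) and a regression of binding on a cognitive score with no demographic term. Assumed, because the documents give no values: the correlation *a* of a demographic factor with binding, its correlation *b* with the raw-based score, and a two-sided 5% test.

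**1. Factor related to both binding and score, no tau-cognition link otherwise.** The induced correlation is r = a × b. By the Fisher approximation, the shift in the test statistic is δ = atanh(|r|) × √(n − 3), and the rejection probability is P(Z > 1.96 − δ) + P(Z < −1.96 − δ).

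For a = 0.3, b = −0.3: r = 0.3 × (−0.3) = −0.09; δ = 0.0902 × √57 = 0.681; rejection probability = P(Z > 1.279) + P(Z < −2.641) = 0.100 + 0.004 = 0.105.

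| a | b | r = a × b | False positives, approximation | False positives, simulation (20,000 runs) |
|---|---|---|---|---|
| 0.2 | −0.2 | −0.04 | 6.1% | 5.8% |
| 0.3 | −0.3 | −0.09 | 10.5% | 10.7% |
| 0.3 | −0.5 | −0.15 | 20.7% | 20.6% |
| 0.5 | −0.5 | −0.25 | 48.7% | 48.7% |

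Replacing the score by its demographically corrected part brings the simulated rate back to about 5% in every row. Entering the factor as a covariate also gives about 5%.

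**2. Factor related to the score only (a = 0).** The false-positive rate stays at about 5%, but a true correlation shrinks to r × √(1 − s), where s is the share of score variance due to the factor. Take a true correlation of 0.40 in absolute size:

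- s = 0: δ = 0.4236 × √57 = 3.198, power 0.89.
- s = 0.20: 0.40 × √0.80 = 0.358, power 0.81.
- s = 0.40: 0.40 × √0.60 = 0.310, power 0.68.

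Simulation with b = 0.3 and 0.5 (s = 0.09 and 0.25) gave mean correlations of −0.38 and −0.34 and power of 87% and 79%, against about 90% with the corrected score.

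**3. Does the z-score reference population matter?** For a single test, standardising to the whole sample or to controls is a linear rescaling, so the correlation with binding is identical. In an illustrative two-test composite the change was from −0.468 to −0.474. The reference should be stated so that the score is reproducible, but it does not drive this point.

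**The case against.** The strongest reply is that silence is not a choice. Section 3.1.2 does not say that the z-scores are uncorrected. A T-score converts linearly to a z-score, so composites built from the T-scores would comply with the text as written. That stands. A reader might infer that the plan averages raw scores and never uses the T-scores; the documents do not support this. They leave the input open and state no use, and section 4.3 sends all participants' data to a consensus conference, where the T-scores may well inform diagnosis.

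A reader might also infer that standardising over a half-impaired sample distorts the composites by down-weighting memory tests. The third step of the check shows that this barely moves the result, and it forms no part of the point.

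Age and education are not ignored: a post-hoc analysis is planned. But it concerns binding and is not linked to the cognition regression, and sex and test language appear in no model.

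There is also a question of estimand. If age lowers cognition through tau, correcting for age removes real signal. Suppose age acts on cognition only through tau, with a true tau-cognition correlation of −0.40. An age-tau correlation of 0.3 implies an age-cognition correlation of −0.12, and age-correcting the score gives (−0.40 + 0.036)/√(1 − 0.0144) = −0.37. With an age-tau correlation of 0.5 the result is (−0.40 + 0.10)/√(1 − 0.04) = −0.31. This loss is similar in size to the dilution above. It is a fair reason to report both models, not to leave the choice unstated.

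Finally, no norms are named, the minimum battery differs from the full one, and results may come from other protocols, so T-scores may not cover every test. The fix has to allow for this.

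**Conclusion.** The point holds as a gap in specification with a concrete consequence. The input to the composites is unstated, the corrected T-scores have no stated analytic use, and the tau-cognition regression names no age, education, sex or test-language term. If raw-based scores are used, a factor related to both binding and scores confounds the slope, and one related to scores only dilutes it.

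The size rests on assumed correlations. In the middle case (0.3 and −0.3) false positives are about 10% instead of 5%; across the assumed range they run from about 6% to 49%. No inflation arises from a factor unrelated to binding. Corrected scores would not by themselves settle the two-language issue, because language is not in the correction. The primary ANOVA on cognitive status is untouched by how the composites are built. The change should be made, but the point does not threaten the primary result.

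**What to change.** **In 3.1.2**, state the input score and the reference, choosing one of two routes:

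- build the composites from the corrected T-scores of section 4.3, as z = (T − 50)/10; or
- where norms do not cover every test, use raw z composites, name the reference population, and put age, education and sex into the model as covariates.

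Use one metric for all tests within a composite; do not mix T-based and raw z-scores.

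**In 7.2**, name the composites that enter the cognition models, state the demographic adjustment that goes with the chosen route, and add test language (English or Spanish) as a covariate in either case. Report the unadjusted raw-composite model as a sensitivity analysis.

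**Cost.** The change is to wording and needs no new visits or tests, since the demographic data and T-scores are already planned. Norm coverage must be checked test by test and language by language before the route is fixed. The covariates use a few degrees of freedom at n = 60. Some signal is lost if age lowers cognition through tau; the unadjusted sensitivity model lets the reader see how much the adjustment changes the slope.
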